7.2 SECONDARY QUESTIONS

1. Does perioperative loss on POD7 (4-10) correlate to losses at EOS and POD3?
2. Is cumulative perioperative loss of albumin from plasma still positive at hospital discharge (or POD 21) following liver transplantation?
3. Dichotomize patients in two equally sized groups depending on the amount of cumulative loss of albumin from plasma on EOS, POD3 and POD7 respectively, i.e. to a "leaky" and a "less leaky" group. Which factors predict "leakiness" (demographics, bleeding, fluid balance, ascites, ELISAs etc)?

4. Is cumulative perioperative loss of albumin from plasma positive at EOS, POD3 and POD7 (4-10), respectively, after liver transplantation in children? This is the primary question in the children substudy .
5. Does perioperative loss on POD7 (4-10) correlate to losses at EOS and POD3 in children after liver transplantation?
6. Which factors characterize children with large postoperative drain losses after liver transplantation?
7. Does cumulative perioperative loss of albumin from plasma at EOS, POD3 and POD7 (4-10), respectively, differ between adults in need or not in need of prolonged ICU stay, respectively, after liver transplantation? This is the primary question in the prolonged ICU substudy.
8. Which factors predict “need of prolonged ICU stay” after liver transplantation (demographics, bleeding, fluid balance, ascites etc)?
9. How does synthesis rate of albumin develop during prolonged ICU stay?

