8 ENDPOINTS

8.1 PRIMARY ENDPOINT

Cumulative perioperative albumin shift (CPAS) by mass balance at POD 7 (4-10).

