8.2 SECONDARY ENDPOINTS

- A. Cumulated albumin mass balance at EOS, POD 3, and at hospital discharge (POD21)
- B. Indices of inflammation and endothelial dysfunction (such as IL6, syndecan, HBP)
- C. Albumin synthesis rate on POD 4-6 and on POD 7-14 after liver transplantation in adult patients (>18 years) in need of a prolonged ICU stay.

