10 STUDY PROCEDURES

10.1 SCREENING, INFORMATION AND CONSENT

All patients accepted for liver transplantation will be approached when accepted for the operation. They will then be informed orally and in writing about the study and the study-specific procedures by the investigator or co-investigator. Preliminary oral informed consent will be noted in the patient record. The written informed consent will be obtained from the patient (or parent) in connection with the liver transplantation. Preliminary recruitment will likely outnumber the anticipated number of patients that are actually studied due to the emergency nature of the procedure, and the very variable time from acceptance to the operation. Albumin mass balance will start in the operating room and continue until hospital discharge or POD21.

Three different versions of the study information will be used.

Adults can participate in all measurements

Children can only participate in albumin mass balance and ELISAs, and parents and children over 12 years will have two different study informations. Children below the age of twelve will only be represented by their parents.

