17.2 STATISTICAL ANALYSIS

In a previous study on selected patients undergoing liver transplantation at our department, we found a net leakage of albumin of 37 ± 17 g at end of surgery and of 48 ± 33 g at the third postoperative day. In our hospital, post-operative albumin infusions to keep plasma albumin at 25 g/l are very common, suggestive of ongoing losses in this patient group.

The effect and time course of ischemic liver injury on albumin synthesis has not been investigated, but in the previous pilot study albumin synthesis was higher than normal values on post-operative day 3. All data will be presented as mean with standard deviation (SD) or as median and range of data if not normally distributed.

Furthermore, the mutual correlations between the mass balance albumin parameters and albumin synthesis and P-albumin will be calculated and presented with correlation coefficients. Patients will be dichotomized to “leaky” and “not so leaky”, and possible predictors analyzed by univariate and multivariate logistic regression.

With 103 subjects there is a power of 80% to detect an anticipated effect size of 0.11 with 3 predictors and a 2-sided significance level of 5%. This equals the situation where the 3rd predictor gives an increase in the squared correlation coefficient r^2 from 0.30 to 0.37 or from 0.50 to 0.54. Although this is rather hypothetical it seems likely that such inferences might occur, and we will find them if 2 years production of liver transplants are investigated. If only 2 predictors are used an effect size of 0.095 can be found with 80% power.

Correlations will be reported as Pearson's correlation coefficient r or Spearman's rank correlation r_s depending on the data's nature.

Demographic preoperative data such as age, height, weight, BMI, gender, routine lab, history of weight loss, diagnoses, and current medications will be presented as numbers, averages and standard deviation, or as median range as applicable.

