17.3 DETERMINATION OF THE NUMBER OF SUBJECTS

On page 4 we state that the number of subjects is 240 in the main study. This refers to an overestimation of the total number of liver transplantations during a approximately 2 year period at our hospital and the primary outcome of albumin mass balance.

The primary endpoint of the study (cumulative perioperative albumin shift at POD7) has never been investigated before. On POD3 48 ± 33 g, $p=0.0017$ versus baseline was found in our previous study on selected patients undergoing liver transplantation [Amouzandeh 2017]. This corresponds to a effect size of 1.4. Although data in consecutive patients are likely to be even more scattered a power of 90% is reached with $n=100$ for an effect size of 0.33 with a one sample 2-sided t-test and a significance level of 5%.

We plan to do linear regression with the thus detected “leakiness” as dependent variable and look at possible predictors. We will also dichotomize the patients in “leaky” and “not so leaky” (cut off to be estimated by ROC-curve analysis) and explore possible predictors by logistic regression and multiple logistic regression. The size of the data base becomes important to the quality of the multiple regression procedure, but data quantity will be governed by our patient flow and research resources. Data collection over much more than 2 years is likely to be confounded by changes in routines over time.

The large number of correlations mentioned above must be seen against the background that this is an exploratory pilot study of albumin mass balance and albumin kinetic parameters in liver transplantation. Because this is an unselected patient group for this kind of measurements, there is an intention that the study also should be hypothesis generating.

Sub study A (children, n=20) is included in the above mentioned number.

Sub study B (prolonged ICU stay, n=20) is a cohort included in the main study above.

The expected numbers in substudies A and B are the main reason to extend the whole study to approximately 2 years, and are based on historical records. Although data are likely to be scattered, with n=10-20 there is a reasonable chance to perform statistical inference analysis. The groups will also be compared with the complete data set.

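### Questions 1 and 5 correlate the POD7 total with early losses it already contains, so a positive r does not show that early loss predicts later loss

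*Combined protocol and SAP*

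**What the plan says.** Question 1 in section 7.2 reads: "Does perioperative loss on POD7 (4-10) correlate to losses at EOS and POD3". Question 5 asks the same in the children's sub study: "Does perioperative loss on POD7 (4-10) correlate to losses at EOS and POD3 in children after liver transplantation".

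The quantities are cumulative. Section 8.1 defines the primary endpoint as the cumulative shift (CPAS) at POD7, with a window of POD 4 to 10. Section 8.2 lists "Cumulated albumin mass balance at EOS, POD 3, and at hospital discharge (POD21" among the secondary endpoints. Section 10.1 says: "Albumin mass balance will start in the operating room and continue until hospital discharge or POD21". Nothing in the text resets the balance at EOS or POD3.

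For the analysis, section 17.2 says that correlations will be given as Pearson's or Spearman's coefficient, depending on the data. The text defines no loss over an interval (EOS to POD3, or POD3 to POD7), no reference value for r other than the usual zero, and no adjustment for overlap. Section 17.3 does plan linear regression with leakiness as the dependent variable, but does not link it to questions 1 and 5. Section 6.1 words the related aim as a comparison of the POD7 loss with the EOS and POD3 losses.

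**The concern.** On a running balance, POD7 CPAS equals POD3 CPAS plus the change after POD3, and POD3 CPAS equals EOS CPAS plus the change after EOS. Questions 1 and 5 therefore correlate a whole with its own parts. For such a pair, zero is not the value that means no relation between early and later loss, because the shared part alone makes r positive.

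The risk is in the interpretation. A paper that reports a clear positive r will be read as showing that patients who leak early go on to leak. The coefficient cannot separate that from overlap. A larger sample does not help, since it only makes the built-in value more certain to appear. The children's sub study carries the same problem, and section 22 plans to publish it separately.

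**Working it through.** **Inputs.** Pilot results (section 17.2): "net leakage of albumin of 37 ± 17 g at end of surgery and of 48 ± 33 g at the third postoperative day". Sample sizes (section 17.3): n = 100 in the power statement, and n = 20 children. The POD7 SD is not available: "The primary endpoint of the study (cumulative perioperative albumin shift at POD7) has never been investigated before". It is therefore an assumption, shown as a range.

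**The plan's own figure.** No expected r, sample size or power is stated for questions 1 and 5. The nearest figure is 90% power for a one-sample two-sided t-test with n = 100, effect size 0.33 and 5% significance. The noncentral t gives 90.5%, so it reproduces. It serves here only to support n = 100.

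**Reference value of r.** Write POD7 = early + D. If D is independent of the early value, cov(early, POD7) = SD(early)², so

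r = SD(early)² / [SD(early) × SD(POD7)] = SD(early)/SD(POD7).

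**Assumed POD7 SD of 45 to 60 g, D independent of early loss:**

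| Pair | r | Significant, n = 100 | Significant, n = 20 |
|---|---|---|---|
| POD3, POD7 | 33/45 = 0.73 to 33/60 = 0.55 | 100% | 98% to 75% |
| EOS, POD7 | 17/45 = 0.38 to 17/60 = 0.28 | 98% to 83% | 38% to 23% |

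The percentages are simulated, and apply if someone tests r = 0 at the two-sided 5% level.

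**Second route to the POD7 SD.** The pilot SDs give an EOS-to-POD3 increment variance of 33² − 17² = 800 (SD 28.3 g), if that increment is independent of EOS. Assume the same variance per day continues:

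- At day 7 the later increment has SD √(4 × 800/3) = 32.7 g, and SD(POD7) = √(33² + 32.7²) = 46.4 g.
- Then r = 33/46.4 = 0.71 for POD3 and 17/46.4 = 0.37 for EOS.
- In 20,000 simulated studies these were significant in 100% and 97% at n = 100, and in 96% and 36% at n = 20.
- Over the permitted window, r for POD3 runs from 0.90 (day 4) to 0.61 (day 10), and r for EOS from 0.46 to 0.31.

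The built-in r for POD3 falls below 0.5 only if the later increment SD exceeds 33 × √3 = 57 g.

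**If early loss returns to plasma.** Let the correlation between POD3 CPAS and the later change be ρ, with increment SD 32.7 g. At ρ = −0.5, r(POD3, POD7) is 0.51; at ρ = −0.7 it is 0.40. So r can be clearly positive while patients with larger early loss lose less afterwards.

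**What the slope does instead.** The slope of POD7 on POD3 is 1 + ρ × 32.7/33. It is 1 when ρ = 0, 0.50 at ρ = −0.5 and 0.31 at ρ = −0.7. It reaches 0 when early loss is fully offset. The same null simulation, correlating early loss with the change after it, gave mean r of 0.00 and 4.8% to 5.0% significant at both sample sizes.

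**Precision of the slope** (day-7 case, slope 1). The 95% half-width is t × residual SD / [SD(early) × √(n − 1)]:

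- POD3: 1.98 × 32.7/(33 × 9.95) = 0.20 at n = 100; 2.10 × 32.7/(33 × 4.36) = 0.48 at n = 20.
- EOS, residual SD √(800 + 32.7²) = 43.2 g: 1.98 × 43.2/(17 × 9.95) = 0.51 at n = 100; 2.10 × 43.2/(17 × 4.36) = 1.22 at n = 20.

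**The case against.** **The answer need not be yes.** A reader might infer that a positive r is guaranteed whatever the biology. The documents do not support that. Section 6.1 asks whether the shift has normalised by POD7, section 6.2 plans to study lymphatic return, and section 5.2 contrasts the persisting pilot loss with major abdominal surgery. If early loss were fully returned, r would be near 0, so r = 0 does have a physiological meaning here. This stands, and it is why the slope needs two reference values.

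**EOS is the weaker case.** A reader might also infer a strong built-in r for EOS. It is only moderate, and in 20 children usually not significant. The higher value of 17/33 = 0.52 is the only one that follows from the protocol's SDs alone, but it concerns EOS against POD3, which neither question asks about. Nor does the protocol propose EOS CPAS as a marker.

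**No test of r = 0 is stated.** Section 17.2 promises coefficients. The significance rates above describe what a conventional test would do. This stands, but both questions ask whether the losses correlate, and zero is the value a reader will compare r with.

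**Increments are coupled too.** Early loss against later minus early contains the early value with a minus sign. If the totals were unrelated, r would be −17/√(17² + 33²) = −0.46 for EOS against POD3 minus EOS, and −0.59 to −0.48 for POD3 against POD7 minus POD3 with the assumed SDs. This stands against replacing the totals by increment correlations alone.

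**The study is exploratory.** Section 17.3 says so, and it offers this as background to the large number of correlations. That speaks to chance findings, not to a systematic shift in r. If the aim is only to estimate the POD7 total from an early total, the overlap is harmless, but the documents do not say that this is the aim.

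**Conclusion.** The point holds in a limited form. As planned, the coefficients for questions 1 and 5 cannot separate prediction of later loss from overlap. With no relation between early and later loss, r would be about 0.55 to 0.73 for POD3 and 0.28 to 0.38 for EOS.

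These sizes rest on an assumed POD7 SD of 45 to 60 g, on independence of early and later loss, and on pilot SDs from a small, selected group. The reported 48 ± 33 g with p = 0.0017 fits only about 9 or 10 patients. The SDs in children may also differ; for r, only the ratio SD(early)/SD(POD7) matters. The direction does not depend on these figures: under independence r is above 0.

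The questions are secondary, and the primary endpoint, sample size and data collection are untouched. Should fix; cheap improvement.

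**What to change.** In section 7.2 (questions 1 and 5), say whether the interest is in the POD7 total or in later loss. In section 17.2, for EOS and POD3 separately:

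- Regress POD7 CPAS on the early CPAS and report the slope with a 95% CI.
- State two reference values. Slope 1 means later loss is unrelated to early loss; above 1, early leakers go on to lose more. Slope 0 means the POD7 total no longer depends on early loss, because it has returned.
- The increments POD7 − EOS and POD7 − POD3 may be shown as an equivalent display (their slope is the above minus 1).
- If r between totals is still reported, print SD(early)/SD(POD7) beside it and do not interpret r > 0 as prediction of later loss.

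The cost is wording only; no new samples or data are needed. There are two caveats to state. Measurement error in the early value biases the slope below 1 and the increment correlation below 0. For illustration, an assumed 4 g or 6 g error in the EOS value, not carried into later totals, would turn a slope of 1 into 1 − 16/289 = 0.94 or 1 − 36/289 = 0.88. And on the figures above, 20 children cannot separate slope 0 from slope 1 for EOS, so that result should be presented as an estimate only.

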8 ENDPOINTS

8.1 PRIMARY ENDPOINT

Cumulative perioperative albumin shift (CPAS) by mass balance at POD 7 (4-10).

8.2 SECONDARY ENDPOINTS

- A. Cumulated albumin mass balance at EOS, POD 3, and at hospital discharge (POD21)
- B. Indices of inflammation and endothelial dysfunction (such as IL6, syndecan, HBP)
- C. Albumin synthesis rate on POD 4-6 and on POD 7-14 after liver transplantation in adult patients (>18 years) in need of a prolonged ICU stay.

9 STUDY DESIGN

The study is a prospective exploratory study of patient physiologic parameters during and after liver transplantation.

Albumin mass balance is measured during liver transplantation and up to hospital discharge or 21 days after end of surgery, by keeping close track of gains and losses (all subjects). Albumin synthesis is measured by incorporation of ⁵D-phenylalanine during 90 minutes (adults).

Samples for ELISA will be obtained from all patient groups.

All other factors are routinely measured and calculated within the liver transplantation protocol.

10 STUDY PROCEDURES

10.1 SCREENING, INFORMATION AND CONSENT

All patients accepted for liver transplantation will be approached when accepted for the operation. They will then be informed orally and in writing about the study and the study-specific procedures by the investigator or co-investigator. Preliminary oral informed consent will be noted in the patient record. The written informed consent will be obtained from the patient (or parent) in connection with the liver transplantation. Preliminary recruitment will likely outnumber the anticipated number of patients that are actually studied due to the emergency nature of the procedure, and the very variable time from acceptance to the operation. Albumin mass balance will start in the operating room and continue until hospital discharge or POD21.

Three different versions of the study information will be used.

Adults can participate in all measurements

Children can only participate in albumin mass balance and ELISAs, and parents and children over 12 years will have two different study informations. Children below the age of twelve will only be represented by their parents.

10.2 FIRST STUDY DAY

The procedure will be an emergency, except for living donors which occurs mainly in children. The patients arrive at the operating room at Perioperative Medicine and Intensive Care at Karolinska University Hospital Huddinge. Venous and arterial lines will be routinely inserted in connection with anesthesia and used for blood sampling. Mass balance of albumin will be achieved by keeping track of all losses (bleeding and drains) and infusions containing albumin or hemoglobin during and after the surgical procedure and repeated sampling of P-albumin. Mass balance sampling and calculation will continue after the surgical procedure.

In children there is no study specific blood sampling during the surgical procedure. Samples will only be taken from suction bottles, drains, urine, and administered blood products.

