3 ABBREVIATIONS

| Abbreviation | Unit | Explanation |
|---------------------|-------------|---------------------------------------|
| ASR | mg/kg/day | Absolute Synthesis Rate |
| Bq | | Becquerel, radiation dose |
| CPAS | g | Cumulative perioperative albumin loss |
| CRF | | Case report form |
| D ₅ -Phe | | Deuterium labeled phenylalanine |
| FSR | %/day | Fractional Synthesis Rate |
| MELD | | Model for End-Stage Liver Disease |
| MPE | | Mol percent excess |
| POD | | Post operative day |

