5.5 MARKERS OF ENDOTHELIAL INJURY AND INFLAMMATION

The mechanism of albumin loss is not well uncovered but increased capillary leakage in connection with fluid overload and inflammation are likely to contribute. Several substances have been suggested as markers of endothelial injury. Commercial enzyme-linked immunoabsorbant assay (ELISA) kits are available for syndecan-1, hyaluron, heparansulphate etc. They represent components of the glycocalyx that are suggested to be flaking in inflammation or injury. Heparin binding protein has been suggested as a mediator of capillary leakage and is also measured by ELISA. Interleukins 6, 8 and 10 are early markers of inflammation and are likewise measured by ELISA. CRP is a too slow parameter to be of relevance in this context, but will be routinely measured and presented.

The field is rapidly developing and possible new ELISAs in the field of glycocalyx function, injury or inflammation might be considered for this investigation.

The blood sampling volume for one measurement by ELISA will be 4 mL for adults and 2 ml for children. This is the only blood sampling in children.

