10.3 POSTOPERATIVE STUDY DAY 1-21 OR TO HOSPITAL DISCHARGE

Mass balance sampling and calculation will continue up to hospital discharge or at most for 21 days after the surgical procedure. POD 1 ELISAs will be taken in all study patients. POD 4 also in adults not in the ICU.

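### The POD 1 ELISA, the only one common to all patients, has no hour or window after end of surgery in the supplied text, and the analysis plans no adjustment for sampling time

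*Combined protocol and SAP*

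**What the plan says.** Timing. Section 10.3 states "POD 1 ELISAs will be taken in all study patients" and then "POD 4 also in adults not in the ICU". Section 10.4 adds a sample for adults in the ICU alongside the albumin synthesis measurement, and allows further samples in children in the ICU. POD 1 is therefore the only draw that every patient has. The abbreviation list expands POD as "Post operative day" and gives no counting rule for surgery that crosses midnight.

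Urgency. Section 10.2 says "The procedure will be an emergency, except for living donors which occurs mainly in children". Section 10.1 refers to "the emergency nature of the procedure, and the very variable time from acceptance to the operation". Neither section gives the hour at which operations start or end.

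Markers. Section 5.5 says "Interleukins 6, 8 and 10 are early markers of inflammation and are likewise measured by ELISA", and it sets CRP aside as too slow for this purpose. It gives no half-life for any marker.

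Use. Secondary endpoint B in section 8.2 is made up of these indices. Question 3 in section 7.2 lists the ELISAs among the candidate predictors of leakiness at end of surgery, POD 3 and POD 7. Sections 17.2 and 17.3 plan linear and logistic regression and name no covariate for sampling time.

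**The concern.** A day label does not fix elapsed time. When surgery ends at unplanned hours, two patients sampled under the same label can be at quite different points after the surgical insult. If a marker changes within hours, part of the variation between patients is then due only to when the blood was drawn.

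That variation has two effects. It widens the spread of endpoint B, and it weakens any true relation between a POD 1 marker and leakiness, so a real predictor is more likely to be missed. The plan chose the interleukins because they respond early, so elapsed time is a natural thing to control for them. The supplied text does not say that the ELISA draw time is recorded, and a time that was not recorded may not be recoverable later.

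**Working it through.** **The plan's own figure.** Section 17.2 gives 80% power for N=103, effect size f² = 0.11 and 3 predictors. With noncentrality 0.11 × 103 = 11.33 and 3 and 99 degrees of freedom, the noncentral F gives 0.7995. The figure reproduces and is not in dispute.

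**Elapsed time (assumed).** Suppose end of surgery is uniform over 24 h, POD 1 is the next calendar day, and blood is drawn at 06:00.
- Surgery ending at 23:00 gives 7 h. Surgery ending at 01:00 gives 29 h.
- The range is 6 to 30 h, with SD = 24/√12 = 6.93 h.
- A draw at any hour of POD 1 would widen this to 0–48 h, with SD = 24/√6 = 9.80 h.

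**Inputs not in the documents (assumed).** Half-life h = 6, 12 or 24 h; between-patient SD s of the log marker = 0.8 or 1.5; true correlation with leakiness 0.30; elapsed time unrelated to the patient's true level. Only n=103 comes from the plan.

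**Formulas.**
- SD due to timing on the log scale = ln2 × 6.93/h, which is 0.80, 0.40 and 0.20.
- Reliability = s²/(s² + timing SD²).
- Observed r = 0.30 × √reliability.
- Power = Φ(atanh(r) × √(103 − 3) − 1.96).

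Without timing noise, atanh(0.30) × 10 = 3.095 and power is Φ(1.135) = 87%.

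| Half-life | Fold change over 24 h | s = 0.8: reliability, r, power | s = 1.5: reliability, r, power |
|---|---|---|---|
| 6 h | 16 | 0.50, 0.21, 58% | 0.78, 0.26, 77% |
| 12 h | 4 | 0.80, 0.27, 79% | 0.93, 0.29, 85% |
| 24 h | 2 | 0.94, 0.29, 85% | 0.98, 0.30, 87% |

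**Cross-check in the plan's own model.** Take the 3-predictor test with R² = 0.11/1.11 = 0.099, let the marker carry the whole effect, multiply R² by the reliability and set s = 1.0. For half-lives of 4, 8, 12, 24 and 48 h, the 80% becomes 37%, 64%, 72%, 78% and 79%. The pattern is the same.

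**Effect of a window.** A tolerance of ±3 h has SD = 6/√12 = 1.73 h. At s = 0.8, power is then 85%, 87% and 87% for half-lives of 6, 12 and 24 h.

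**The case against.** The strongest objection is that the missing hour cannot be confirmed. The contents list a flow chart in 25.1, which is not in the supplied text and is a natural place for sampling times. This stands, and the point is worded accordingly. It does not remove the point, because section 17 would still have no term for sampling time.

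A reader might also infer more than the documents support:
- *That operations end at all hours.* The text says only that they are emergencies with a variable wait. The waiting time in section 10.1 is not a clock time.
- *That living-donor cases are sampled at systematically different times from the rest.* No section says that planned operations end at more regular hours. These cases are mainly among about 20 children (section 17.3), where any such difference would be confounded with age. No child–adult marker comparison is specified.
- *That every marker changes fast.* The word early is applied only to IL-6, IL-8 and IL-10. Nothing is said about the kinetics of syndecan-1 or heparin binding protein.

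The power figures rest on assumptions, and 58% needs both the shortest half-life and the smaller SD. A single correlation is not exactly the planned analysis: n=103 belongs to a 3-predictor regression, and question 3 dichotomises the outcome. Section 17.3 does also plan linear regression on leakiness, so the correlation is a fair guide to direction and order of size. If about 200 patients were studied (almost 100 a year for about 2 years), the worst case shown would still have 86% power, against 99% without timing noise. Section 17.3 also calls the study exploratory and hypothesis generating.

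**Conclusion.** The point holds in a limited form. In the supplied text the POD 1 draw has neither an hour nor a window after end of surgery, and no adjustment for sampling time is planned. Since most operations are unplanned, the label allows a spread of about 24 h; the documents do not show what spread will occur. A timing difference between living-donor cases and the rest is possible but not shown.

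At n=103 the loss of power runs from negligible to 29 percentage points (87% to 58%) over the half-lives and SDs tried. It matters only for markers that halve in about 12 h or less. It bears on endpoint B and on the marker predictors in question 3. The primary endpoint, CPAS at POD 7, does not use the ELISAs and is untouched. This is a cheap improvement to exploratory analyses, not a flaw in the main result.

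**What to change.** Record the exact date and time of each ELISA draw and of end of surgery in the CRF. In section 17.2, state that marker analyses use the log marker with hours since end of surgery as a covariate, in both the linear and the logistic models, and that the distribution of those hours is reported with endpoint B. If a plot shows that the log marker is not close to linear in time, allow a curved term.

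Where feasible without extra staff, also state in section 10.3 a target interval and tolerance after end of surgery for the first draw. The ±3 h used in the working is an illustration. If the flow chart in 25.1 already carries a sampling time, repeat it in 10.3.

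The cost is one time field and one model parameter (more if a curve is needed), with no extra blood. A window would put some draws outside routine rounds; if that is not acceptable, recording and adjusting can be done without it.
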